Overall, out of the five studies using VR active gaming interventions in youth with ASD, including the previously described studies using some type of control group, three reported it to be beneficial for improving balance and two were inconclusive. Findings from all of these studies are compromised due to 1) lack of randomized controlled trials, 2) lack of objective balance measures, 3) variability in intervention duration, 4) small sample sizes (10-29 subjects), 5) limited game options, 6) lack of clear identification of motor learning/control principles in the research design, (7) variability in game design (i.e. 3 were not commercially available), and 8) no assessment beyond immediate-post intervention. The current published literature does not provide sufficient evidence for the use of VR active gaming as a modality to address postural control/balance deficits in individuals with ASD.

The purpose of this study is to deliver a VR active gaming-based static and dynamic balance intervention to children and youth with ASD that addresses several of the aforementioned gaps in the literature by: 1) using a controlled clinical trial design, 2) using objective measures of static and dynamic balance, 3) using select commercially available VR active games that incorporate specific motor learning principles that impact balance, 4) using a participant sample based on a power calculation to ensure a robust statistical analysis, and 5) assessing retention effects 4 weeks post-intervention. Addressing these gaps will significantly contribute to the knowledge base by verifying if VR active gaming interventions are effective in improving static and dynamic balance in youth with ASD.

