# 7.0 Study Procedures

1. Prior to day 1: Informed consent materials, a screening questionnaire, and Autism Spectrum Screening Questionnaire (ASSQ) will be sent electronically to parents/caregivers. Participants and parents/caregivers in both groups will be given access to a video of the data collection space, intervention space setting, and a short introduction of the research personnel for review. If the participants are 18 years or older, this information will be shared with the participants directly and they will fill the questionnaires. If the participant is less than 18 years old, the information will be shared with the parent/legal guardian to be completed. Additionally, The ASSQ is a commonly used valid and reliable 27-item checklist to be filled in by parent/caregiver for assessing symptom characteristics of ASD. The ASSQ can be completed in 10 minutes using a 3-point Likert scale with possible score range being 0 of 54 with 19 being a cut off for a parent/caregiver rating identifying ASD. This tool will be used as a part of demographic screening of the participants prior to the pre-intervention day and used to better describe individual autism symptoms than is available in a medical or educational diagnosis. The researcher will subsequently contact participants and parent/caregiver to review the information, check for understanding, (particularly the terminology used in the ASSQ), assess eligibility via screening tool and address any other questions prior to study inclusion and visit.

Study participation will require 9 visits: 1 pre-intervention visit, 6 intervention visits, 1 post-intervention visits and 1 retention visit. Participants will receive \$10 Amazon or Kroger gift card after completing each session with total possible compensation of \$90.

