# 2. Pre-intervention/session 1:

2.1 As part of familiarization, participants will be shown and allowed to handle the different data collection instruments and ask questions. The intervention group will be shown the Nintendo Switch to get familiarized with their operation and functions. Parents/caregivers of the participants (under 18 years of age) in the intervention group will be handed over the Nintendo Switch Sports

to be connected at their home for the duration of intervention. Participants 18 years of age or older will be given the device. Researchers will provide any technological assistance required for this purpose.

2.2 Weight will be recorded using a calibrated scale and height measured using a stadiometer. The Edinburgh Handedness Inventory-short form (EHI-SF) will be used to assess hand-preference. It is a valid and reliable 4-item checklist of everyday tasks and participants score their hand preference on 5-point Likert scale (for each item, always right= 100, usually right= 50, usually left= 50, always left= -100). A researcher will read the rating scale to those with low literacy level. Handedness will be determined using a laterality quotient. The laterality quotient is interpreted as left handers (-100 to -61), mixed handers (-60 to +60) and right handers (61 to 100). Hand length will be calculated using a tape cloth, measured from greater tuberosity to distal end of middle digit on the right hand and leg length iliac crest to ground on the right leg.

Participants will be shown the different data collection instruments to handle, get familiarized and ask questions. Participant's hand dominance will be recorded using the Edinberg Handedness Inventory-short form. Participant's foot dominance will be recorded by asking them to kick an imaginary ball placed on the ground in front of them. Practice trials for balance and gait assessments will be conducted to ensure understanding of the protocol. Baseline assessments for posture and gait will be performed.

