## 4. Post-intervention/session 8 and 9:

Static and dynamic balance will be reassessed as previously described to examine retention effects of the VR active gaming intervention (see study calendar). Session 8 will be at least 3-5 days after session 7. Parent/caregiver will return the Nintendo Switch Sports to the researcher. Session 9 will be 4 weeks after session 7. Each session will be for approximately 60 minutes.

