# 11.0 Statistical Considerations

According to prior research study examining the similar paradigm using Xbox games (Ghobadi et al. 2019), we predict the medium effect size (f=0.25) to detect significant changes within groups, between groups and effect of timepoint on static and dynamic balance. Power analysis

(using G\*power 3.1.9.7 software) indicates 14 subjects in each group to have 0.8 power to detect this effect (alpha 0.05). To account for the likelihood of attrition and noncompliance, total 40 participants are being recruited. Data from participants who engage in all the intervention sessions will be included in the analysis.

SPSS (Statistical Package for the Social Sciences) and MATLAB will be used for processing and analyzing the data. Participants demographic and health characteristics will be compared using paired sample t-tests. Intention to treat analysis will be used for addressing effects of treatment or control on static and dynamic balance. The dependent variables for static balance include: 1) sway area of 95% confidence ellipse for center of pressure(mm²), 2) direction of center of pressure sway as anteroposterior and mediolateral (mm). The dependent variables for dynamic balance are: 1) step length (m), 2) stride length (m), 3) step width (m), 4) double support period (sec), 5) cadence (steps/min) and 6) gait velocity (meters/min). Total PBS score will be dependent variable for both static and dynamic balance.

Two-way repeated measures ANOVA (analysis of variance) will be used to determine 1) within intervention and control group, for assessing the main effect of group, 2) between intervention and control group for assessing main effect of time, and 3) between - within interaction for assessing the interaction term. Statistical significance will be declared if  $p \le 0.05$  (two-tailed).

[name] ([contact]) will assist with the statistical considerations.

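### Section 11.0 plans no baseline-adjusted VR-minus-exercise difference after training or at 4 weeks; the interaction is valid but omnibus, and the three-visit group effect is not the treatment effect

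*Combined protocol and SAP*

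**What the plan says.** The whole analysis of treatment effect is one sentence in section 11.0. It begins "Two-way repeated measures ANOVA (analysis of variance) will be used to determine" and lists three tests: one "for assessing the main effect of group", one for time, and the "between - within interaction for assessing the interaction term". It does not list the levels of time. It mentions no baseline covariate, change score, planned contrast or main time point.

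The visits are clear elsewhere. Section 7.0 states: "Study participation will require 9 visits: 1 pre-intervention visit, 6 intervention visits, 1 post-intervention visits and 1 retention visit". At session 1, "Baseline assessments for posture and gait will be performed". For sessions 8 and 9, "Static and dynamic balance will be reassessed as previously described to examine retention effects of the VR active gaming intervention". The calendar in section 8.0 places session 8 at 3 to 5 days, and session 9 at 4 weeks, after the last training session.

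Both specific aims in section 2.1 compare VR gaming with traditional balance exercises, and section 1.0 lists "assessing retention effects 4 weeks post-intervention" among the study's purposes. The sample size rests on this sentence in section 11.0: "we predict the medium effect size (f=0.25) to detect significant changes within groups, between groups and effect of timepoint". With power 0.8 and alpha 0.05 it arrives at 14 per group.

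**The concern.** Session 1 comes before training, so no training difference between arms can exist there. If it enters the ANOVA as an ordinary level of time, the group main effect averages a zero in with the two post-training differences. Someone who reads that test as the answer on treatment could conclude that VR is no different from exercise when it is.

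The interaction avoids this, but it only says that the two profiles differ somewhere. It does not say whether VR was better just after training, at 4 weeks, or only in the change between those visits. The comparator is active training and 40 people are planned. The report would then have p-values but no planned estimate, with its uncertainty, of the quantity each aim asks about.

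**Working it through.** **Inputs.** From section 11.0: f = 0.25, alpha 0.05 two-sided, power 0.8, 14 per group. From sections 7.0 and 8.0: two arms and three balance assessments. The correlation r between visits is not stated, so r = 0.5 is assumed, with 0.3 to 0.8 shown. Equal SDs and equal correlations across visits are also assumed.

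**1. The plan's own figure.** For the group-by-time interaction, λ = f²·N·m/(1 − r) = 0.0625 × 28 × 3/0.5 = 10.5 on 2 and 52 df. Power is 0.81, so 14 per group reproduces. At r = 0.5, two measurements would need N = 34 and four would need N = 24. With three measurements, r = 0.3 would need 38 and r = 0.7 would need 18. For the between-groups test, λ = f²·N·m/(1 + 2r) = 0.0625 × 28 × 3/2 = 2.625, power 0.345; it would need N = 86. The sample size therefore fits the interaction with session 1 as one of three time levels.

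**2. The group main effect.** With random allocation the expected session-1 difference is 0. The main effect estimates (0 + d8 + d9)/3, against a mean post-training difference of (d8 + d9)/2. The ratio is (1/3)/(1/2) = 2/3, whatever d8, d9 and r are.

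**3. The interaction.** It has (2 − 1)(3 − 1) = 2 df. For a sustained effect (0, d, d), the squared deviations sum to d²(4/9 + 1/9 + 1/9) = 2d²/3, so λ = (2d²/3)(n/2)/(1 − r) with n per arm. Setting this equal to f²·2n·3/(1 − r) gives d² = 18f² = 1.125, so d = 1.06 SD. That is the plan's own f on this scale.

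**4. Power at an assumed 0.8 SD, sustained, 14 per arm.** For the 1-df tests, λ = δ²·n/(2v):

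- group main effect: δ = 2d/3, v = (1 + 2r)/3, 26 error df
- session 8 adjusted for session 1: δ = d, v = 1 − r², 25 error df
- adjusted mean of sessions 8 and 9: δ = d, v = (1 + r)/2 − r², 25 error df

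At r = 0.5 the λ values are 2.99 (group), 0.4267 × 7/0.5 = 5.97 (interaction), 0.64 × 7/0.75 = 5.97 (session 8) and 0.64 × 7/0.5 = 8.96 (mean).

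| r | Group effect | Interaction | Session 8 adjusted | Mean of 8 and 9 adjusted |
|---|---|---|---|---|
| 0.3 | 0.46 | 0.42 | 0.57 | 0.78 |
| 0.5 | 0.38 | 0.56 | 0.65 | 0.82 |
| 0.7 | 0.33 | 0.79 | 0.81 | 0.92 |
| 0.8 | 0.31 | 0.93 | 0.92 | 0.98 |

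At r = 0.5 the interaction and the session-8 contrast have the same λ, so that gain comes only from testing one contrast instead of two. With 20 per arm at r = 0.5 the row is 0.52, 0.73, 0.81, 0.94. At the plan's own 1.06 SD with 14 per arm it is 0.60, 0.81, 0.88, 0.97.

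**5. Other effect patterns (r = 0.5, 14 per arm).**

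| Effect at session 8, session 9 (SD) | Interaction | Session 8 adjusted | Mean adjusted |
|---|---|---|---|
| 0.8, 0.4 | 0.44 | 0.65 | 0.58 |
| 0.8, 0 | 0.56 | 0.65 | 0.30 |
| 0.4, 0.8 | 0.44 | 0.22 | 0.58 |

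**The case against.** The strongest reply is that the plan does not depend on the diluted test. The interaction is a valid test of differential change. It uses baseline through the within-person comparison, and it is the test that 14 per group fits. At the plan's own f and r = 0.5 it has power 0.81 with 28 people and 0.94 with 40. This stands. A reader might infer that the trial's test of treatment loses a third of its effect, or that the plan misses its own power target. The documents support neither.

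A second reply is that the trial asks about two times, after training and at 4 weeks. Two post-baseline differences make a 2-df question, and the interaction is their global test. This also stands. A reader might infer that the interaction wastes a degree of freedom, but no main time point is named, so the documents do not support that. What the global test lacks is an estimate at either visit.

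Third, choosing session 8 is a judgement. It loses if the effect builds (0.22 against 0.44). If both contrasts were tested as equals at 0.025, session-8 power would be 0.53, below the interaction's 0.56 (r = 0.5, 0.8 SD sustained, 14 per arm). An order of testing is therefore needed.

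Finally, section 11.0 does not say that session 1 is a time level. That is an inference, though a strong one. If session 1 were left out, the dilution would go, but the ANOVA would make no use of baseline at all.

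**Conclusion.** The point holds as an omission with a cheap remedy; the planned interaction is not in error. Two parts need no assumed correlation. No planned test yields a VR-minus-exercise difference at session 8 or session 9. And if session 1 is a time level, the group main effect falls exactly one third short of the mean post-training difference, given an expected baseline difference of zero.

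The power gain is conditional. For 0.8 SD sustained and 14 per arm, the session-8 contrast gains 9 points at r = 0.5 and 2 at r = 0.7, and nothing at r = 0.8. The larger figures for the adjusted mean (0.82, 0.92, 0.98) belong to a different contrast, which falls to 0.30 at r = 0.5 if the effect is gone by session 9. The 0.8 SD, the equal SDs and the equal correlations are assumptions. The main reason to change is that the results would answer the aims with estimates; power is secondary.

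**What to change.** In section 11.0, replace the ANOVA sentence for each outcome with a model that:

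- takes sessions 8 and 9 as the outcomes, with arm, visit and arm-by-visit as terms and the session-1 value of the same variable as covariate;
- reports the baseline-adjusted VR-minus-exercise difference with a 95% CI at session 8 (main contrast, tested first at 0.05) and at session 9 (retention contrast, tested only if the first is significant).

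State that a three-visit group main effect, if shown, is not the treatment effect. Restate the power calculation for the session-8 contrast, with the assumed correlation written down.

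The cost is one paragraph plus the new power statement. No new data are needed, and SPSS, already named, can fit the model. The downside is the commitment to session 8: if the effect appears mainly by session 9, the main contrast loses power and the testing order also blocks the retention test. If the sponsor expects that pattern, the main contrast should be chosen accordingly before any outcome data are seen. The order protects the error rate across the two visits within one outcome, not across the several outcomes.

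### Retention at 4 weeks is a stated purpose, but section 11.0 plans only omnibus ANOVA effects, none of which isolates session 9

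*Combined protocol and SAP*

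**What the plan says.** **Purpose.** Section 1.0 gives five ways in which the trial addresses gaps in the literature, and the fifth is "assessing retention effects 4 weeks post-intervention". Section 7.0, item 4, says: "Static and dynamic balance will be reassessed as previously described to examine retention effects of the VR active gaming intervention".

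**Assessments.** There are three. At session 1, "Baseline assessments for posture and gait will be performed". Then "Session 8 will be at least 3-5 days after session 7", and "Session 9 will be 4 weeks after session 7". Sections 8.0 and 14.0 repeat this timing, and section 14.0 describes sessions 8 and 9 as follow-up and retention assessments.

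**Analysis.** Section 11.0 states "Two-way repeated measures ANOVA (analysis of variance) will be used to determine 1) within intervention and control group" and goes on to list a main effect of group, a main effect of time, and the "between - within interaction for assessing the interaction term". Each is judged at p ≤ 0.05, two-tailed. The section names no contrast, post-hoc comparison, session-9 comparison or rule for retention. It does not list the levels of the time factor. The endpoints in section 3.2 carry no time point.

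**The concern.** With three assessments, the time and interaction terms each have 2 degrees of freedom. They ask whether anything differs across the three visits, not which visit differs. A gain at session 8 that has vanished by session 9 violates the null of the interaction test just as a lasting gain does. The group main effect averages over all three visits, baseline included, so it does not isolate session 9 either.

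At stake is one of the trial's five declared contributions. Session 9 will be run and its data entered, but no planned test says whether VR differs from exercise 4 weeks after training, or whether the VR gain persists. Any follow-up comparison would have to be chosen after the data are seen.

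**Working it through.** **Inputs.** From section 11.0: f = 0.25, alpha 0.05 two-sided, power 0.8, 14 per group, 40 recruited (20 per arm under section 6.0). From sections 7.0 and 8.0: m = 3 assessments. Assumed, because the documents give no figure: equal correlation r = 0.5 between visits (range 0.3 to 0.7), SD 1 at each visit, sphericity.

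**1. The plan's own figure.** For the interaction in a two-group repeated measures ANOVA, λ = f²·N·m/(1 − r), with (m − 1) and (N − 2)(m − 1) degrees of freedom.
- m = 3, r = 0.5, N = 28: λ = 0.0625 × 28 × 3/0.5 = 10.5 on 2 and 52 df; power 0.812. This reproduces 14 per group.
- m = 2, r = 0.5: power 0.721 at N = 28, and 17 per group are needed.

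The stated sample size therefore fits a three-visit omnibus test at r = 0.5. It does not prove three levels: m = 2 with r = 0.6 also gives 0.813 at N = 28.

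**2. Loss and retention give the same f.** Let the VR-minus-exercise difference be d at session 8.
- Fully lost, (0, d, 0): deviations from the mean are (−d/3, 2d/3, −d/3); sum of squares 6d²/9.
- Fully kept, (0, d, d): deviations are (−2d/3, d/3, d/3); sum of squares 6d²/9.

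In both cases f = √[(d²/4)(6/9)/3] = d/√18. Setting f = 0.25 gives d = 0.25 × 4.243 = 1.06 SD. Under compound symmetry, equal f means equal λ and equal rejection probability.

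**3. Probability that the interaction is significant, the same for full loss and full retention.**

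| d (SD) | r | 14 per arm | 20 per arm |
|---|---|---|---|
| 1.06 | 0.3 | 0.661 | 0.827 |
| 1.06 | 0.5 | 0.812 | 0.935 |
| 1.06 | 0.7 | 0.962 | 0.995 |
| 0.8 | 0.5 | 0.556 | 0.729 |
| 0.5 | 0.5 | 0.245 | 0.341 |

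A 20,000-run simulation at d = 1.06 and r = 0.5 agrees: 0.812 (loss) and 0.813 (retention) at 14 per arm, 0.932 and 0.937 at 20 per arm. If the exercise arm stays flat, the time effect has the same probabilities. The group main effect does differ between the patterns (r = 0.5): 0.20 and 0.27 under loss, 0.60 and 0.76 under retention, at 14 and 20 per arm.

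**4. A contrast that does isolate session 9.** Compare the arms on change from session 1 to session 9. The SD of change is √[2(1 − r)], which is 1 at r = 0.5.
- Full loss: the true contrast is 0, so it is significant 5% of the time (simulated 5.1% and 4.9%).
- Full retention, d = 1.06: noncentrality 1.06/√(2/14) = 2.81 gives power 0.77 at 14 per arm; 1.06/√(2/20) = 3.35 gives 0.905 at 20 per arm. Over r = 0.3 to 0.7 the ranges are 0.63 to 0.94 and 0.79 to 0.99.

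**5. Non-significance from session 8 to session 9 is not a substitute.** At r = 0.5, a true loss of 0.5 SD is missed within an arm (paired t test) 59% of the time at n = 14 and 44% at n = 20. Between arms it is missed 75% and 66% of the time.

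**The case against.** **Retention has limited standing.** The hypotheses and aims in section 2.1 and the endpoints in section 3.2 do not mention it, and no estimand is given. This stands, and it limits the weight of the point. But retention is a declared purpose with its own visit, so it needs an analysis.

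**The plan does not claim retention from an omnibus test.** A reader might infer that the trial will announce a lasting benefit when nothing was retained. The documents do not support that. No section says that a significant group, time or interaction effect will be read as retention, or that a non-significant difference between sessions 8 and 9 will be. The visit means would also show a complete loss descriptively. What remains is that no planned test addresses the question.

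**The omnibus tests need not be significant after a complete loss.** A reader might take the result as near certain. It is likely only for a large gain over active exercise, about 1.06 SD. At d = 0.5 and r = 0.5 it is about one in four to one in three, and the group effect responds weakly.

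**A session-9 between-arm contrast is not retention as such.** A reader might make it the sole measure. Sections 7.0 and 8.0 give the control arm supervised balance exercises. If both arms gain and both keep the gain, the contrast is zero although the VR gain persisted fully. This objection stands, so within-arm changes are needed alongside it.

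**Three time levels are inferred.** This is true. Three is the natural reading of the schedule. If time had only two levels, one of the scheduled reassessments would fall outside the planned model.

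**Conclusion.** The point holds as a gap between purpose and analysis. Section 11.0 has no test that isolates session 9. The interaction test is equally likely to be significant under full loss and full retention: 0.81 at 14 per arm and 0.935 at 20 per arm for the planned effect at r = 0.5, with ranges of 0.66 to 0.96 and 0.83 to 0.995 over r = 0.3 to 0.7. A significant omnibus result therefore neither supports nor refutes retention.

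The equality rests on three time levels and compound symmetry. The probabilities also rest on the assumed r and d. That no planned effect isolates session 9 depends on neither r nor d. The change should be made, because the data are already to be collected and a direct contrast is available.

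**What to change.** In section 11.0:

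1. List the levels of the time factor (sessions 1, 8 and 9).
2. Prespecify two 1-df between-arm contrasts with 95% CIs: change from session 1 to session 8 (effect at the end of training) and change from session 1 to session 9 (VR versus exercise at 4 weeks).
3. For persistence of the VR gain itself, report within-arm change from session 1 to session 9 and from session 8 to session 9, with 95% CIs.
4. State that neither an omnibus time or interaction effect, nor a non-significant difference between sessions 8 and 9, will by itself be taken as evidence of retention.
5. Designate PBS total score, which section 3.2 labels primary, for the main contrast and treat the other outcomes as supportive. Section 11.0 names ten dependent variables (sway area, two sway directions, six gait measures, PBS), so contrasts for all of them without a hierarchy would multiply the tests.

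Cost: a few sentences and a few more contrasts, with no new visits or participants. The session-9 claim would rest on its own test, which may be non-significant when the omnibus test is significant. For a fully retained effect of the planned size at r = 0.5, its power is about 0.77 at 14 per arm, just under the planned 0.8 (15 per arm would reach it), and about 0.90 at 20 per arm.

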## 2.0 Objectives

# 2.1 Primary Objective

H1: Participation in VR active video gaming incorporating explicit and implicit learning, feedback and knowledge of results, and knowledge of performance motor tenets will lead to increased postural control, as reflected by improved static and dynamic balance. This hypothesis will be tested by Specific Aim 1: to assess the effect of a short-term (3 days/week for 2 weeks) VR active video gaming intervention on static balance, versus traditional balance training exercises, in youth with ASD.

H2: Participation in VR active video gaming incorporating explicit and implicit learning, feedback and knowledge of results, and knowledge of performance motor tenets will reduce the deviation in the spatiotemporal parameters of the gait due to increased dynamic balance and improved motor coordination. This will be tested by Specific Aim 2: to assess the effect of a short-term (3 days/week for 2 weeks) VR active video gaming intervention on spatiotemporal parameters of gait, as a measure of dynamic balance, versus traditional balance training exercises, in youth with ASD.

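### The ANOVA wording swaps the group and time labels and names no effect as the VR-versus-exercise test; the single power statement holds for the interaction only under assumptions it does not state

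*Combined protocol and SAP*

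**What the plan says.** Section 11.0 (Statistical Considerations) describes three parts of the two-way repeated measures ANOVA. The first is "within intervention and control group, for assessing the main effect of group", the second is "between intervention and control group for assessing main effect of time", and the third is the interaction. None is named as the test of H1 or H2.

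Section 2.1 states both aims as comparisons with an active control. Aim 1 concerns the effect of the "VR active video gaming intervention on static balance, versus traditional balance training exercises, in youth with ASD". Aim 2 concerns "spatiotemporal parameters of gait, as a measure of dynamic balance, versus traditional balance training exercises, in youth with ASD". Section 11.0 adds: "Total PBS score will be dependent variable for both static and dynamic balance".

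On sample size, Section 11.0 takes f=0.25 from an earlier Xbox study "to detect significant changes within groups, between groups and effect of timepoint on static and dynamic balance" and reports that the power analysis "indicates 14 subjects in each group to have 0.8 power to detect this effect (alpha 0.05"; 40 are recruited to allow for attrition and noncompliance. No number of measurements, between-visit correlation or sphericity value is given.

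On baseline description: "Participants demographic and health characteristics will be compared using paired sample t-tests".

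**The concern.** With two arms measured repeatedly, group is the between-participant factor and time the within-participant factor. Section 11.0 pairs them the other way round, and the sentence is complete, so lost text does not explain it.

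The swap matters because no effect is designated. Section 7.0 trains both arms, so both may improve. That would produce a time effect with no VR advantage, and it is the time effect that the text attaches to the between-arm comparison. With three effects available and none named, a significant result on any of them could be presented as support for H1 or H2.

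The power sentence adds a second risk. One f and one sample size are given for effects whose power differs widely at the same f. If the group main effect is among them, a null result on it could be read as adequately powered when it is not.

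The paired t-tests are a smaller error and touch only the baseline description.

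**Working it through.** **Inputs.** From Section 11.0: f=0.25, 14 per group (N=28), power 0.8, alpha 0.05, 40 recruited. From Section 7.0: m=3 assessments (Sessions 1, 8 and 9). Assumed, because not stated: equal correlation ρ between visits, shown at 0.3, 0.5 and 0.8, and sphericity (ε=1) unless noted.

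**Formulas.** Power is the probability that a noncentral F(df1, df2, λ) exceeds the 5% critical value.
- Time or interaction: λ = f²Nm/(1−ρ), df = m−1 and (N−2)(m−1).
- Group main effect: λ = f²Nm/(1+(m−1)ρ), df = 1 and N−2.

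**Step 1: reproduce 14 per group.** f²Nm = 0.0625 × 28 × 3 = 5.25. At ρ=0.5, λ = 5.25/0.5 = 10.5 on 2 and 52 df, and power is 0.812. N=28 is the smallest even total reaching 0.80, so the plan's figure reproduces for time or interaction. Two visits with ρ=0.6 also give 28 (power 0.813), so the settings actually used cannot be identified.

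**Step 2: vary the correlation.** For N=40, f²Nm = 0.0625 × 40 × 3 = 7.5.

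| Effect | N | ρ=0.3 | ρ=0.5 | ρ=0.8 |
|---|---|---|---|---|
| Time or interaction | 28 | 0.661 | 0.812 | 0.996 |
| Time or interaction | 40 | 0.827 | 0.935 | 1.000 |
| Group main effect | 28 | 0.415 | 0.345 | 0.278 |
| Group main effect | 40 | 0.560 | 0.471 | 0.381 |

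At N=28, time or interaction reaches 0.80 once ρ is about 0.49 or more. With all 40 analysed, about 0.26 is enough.

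**Step 3: best case for the group main effect.** Its λ falls as ρ rises, so ρ=0 is the most favourable non-negative value. There λ = 5.25 gives 0.597 at N=28, and λ = 7.5 gives 0.761 at N=40. A total of 70, 86 or 112 would be needed for 0.80 at ρ = 0.3, 0.5 or 0.8.

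**Step 4: sphericity.** At ρ=0.5, N=28 and ε=0.75, λ = 0.75 × 10.5 = 7.875 on 1.5 and 39 df, and interaction power falls from 0.812 to 0.722.

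**Step 5: what f=0.25 stands for.** Take a change absent at Session 1 and held at Sessions 8 and 9. The pattern (0, 1, 1) has variance 2/9 over the three visits. In units of the within-arm SD:
- Group: a constant gap of 2f = 0.50 SD.
- Time: a common change of f/√(2/9) = 0.25/0.471 = 0.53 SD.
- Interaction: a VR-minus-control difference in change of 2f/√(2/9) = 0.50/0.471 = 1.06 SD.

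**Step 6: a shared gain.** By Step 5, a 0.53 SD gain in both arms is f=0.25 for time. With 40 participants the time effect would therefore be significant with probability 0.83, 0.94 or 1.00 at the three correlations, although VR adds nothing. In simulations with a shared 0.5 SD gain (N=40, 20,000 trials per cell), the interaction rejected in 0.049 to 0.050 of trials and the group effect in 0.050 to 0.052. Only the time effect is misleading here.

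**Step 7: paired tests.** Section 7.0 takes height, weight, limb lengths and handedness at Session 1, and the Section 8.0 calendar excludes them from Sessions 8 and 9. There is no second measurement on the same person to pair.

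**The case against.** The practical effect is limited. Software labels the effects correctly whatever the SAP says, the interaction is already listed, and it is protected against a shared gain. Misreporting would require the authors to follow a wording slip over their own output. This all stands, and it makes the point a wording correction. It does not supply the missing designation.

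The power sentence also has a benign reading. It speaks of changes between groups and then of a single effect, which can mean a between-arm difference in change, that is, the interaction. On that reading 14 per group is right at a correlation of 0.5, and power with all 40 is higher still. This stands too, so the shortfall for the group main effect is conditional on the other reading.

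A reader might infer more than the documents support:
- *That the sample size is miscalculated or the trial underpowered.* The figure reproduces for the interaction, and no section makes the group main effect the treatment test.
- *That the figure needs a correlation close to 0.5.* It needs at least about 0.49; higher values only help.
- *That Section 1.0 shows shared gains will occur.* It reports one VR study whose investigators only speculated about a test-retest effect, and whose controls rested. The case for a possible shared gain rests on both arms being trained here.

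Finally, Section 6.0 assigns the next participant in the same age range to the other arm, which might seem to create pairs. The plan never defines such pairs for analysis, and its ANOVA compares the arms as independent groups.

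**Conclusion.** The labels are reversed, no effect is designated as the VR-versus-exercise test, and the paired t-tests do not suit two independent arms. These are matters of text and need no assumption.

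The power statement is incomplete and should not be called wrong outright. Given three visits and sphericity, 14 per group supports 0.80 for time or interaction when the correlation is about 0.49 or higher, and falls short below that or when sphericity fails. If the statement is meant to cover the group main effect, it does not hold at any non-negative correlation, even with all 40 recruited.

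The F-tests are unaffected. What is at stake is which result may be claimed as VR against exercise, so the correction should be made before outcome data are seen.

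**What to change.** Revise Section 11.0 as follows.

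1. Correct the labels: between arms is the group effect, within arms is the time effect.
2. Name group by time as the deciding effect for the static outcomes (Aim 1), the gait outcomes (Aim 2) and PBS total, which the plan uses for both kinds of balance. State that a time effect alone does not support H1 or H2.
3. Report with it the VR-minus-control difference in change from Session 1 to Session 8 and to Session 9, because a 2-df interaction test does not show direction.
4. Restate 14 per group as applying to the interaction, giving the number of visits, the assumed correlation, the sphericity assumption or correction, and the difference that f=0.25 represents (about 1.06 SD for a change held at both later visits). Drop any power claim for the group main effect.
5. Replace the paired t-tests with independent-samples tests or a baseline table by arm.

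The cost is wording only: no new data, participants or visits, and no change to the ranking of outcomes. The downside is a less favourable power sentence, which will show a large target difference and its dependence on the assumed correlation and sphericity. A baseline-adjusted contrast at Session 8 would be a reasonable alternative, but it is a preference and not part of this correction.
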